9.2.5 SAEs (Including Deaths) and Adverse Events Leading to Study Drug Discontinuation

SAEs (including deaths) and AEs leading to study drug discontinuation will be summarized by SOC and PT and in listing format.

9.2.6 Adverse Events of Special Interest

Adverse events of special interest (AESI) will be summarized by SOC and PT and will be based on standardized or company MedDRA queries (SMQs or CMQs). AESI are categorized in [Appendix B](#). Tabular listings of AESIs will be provided.

9.2.7 Adverse Events by "Reasonably Possibly Related" Relationship

TEAEs and reasonably possibly related AEs occurring for more than 2% of the subjects in any of the treatment groups will also be summarized by MedDRA SOC and PT. If a subject has an AE with an unknown relationship, then the AE will be counted as 'related.'

9.2.8 Frequent (> 5%) Adverse Events and Reasonably Possibly Related Adverse Events by Preferred Term in Decreasing Frequency

TEAEs and reasonably possibly related AEs occurring for more than 5% of the subjects in any of the treatment arms will be summarized by MedDRA PT in decreasing frequency separately.

9.2.9 Listing of Adverse Events

The following additional summaries of AEs will be prepared.

- Listing of Subjects with Treatment-Emergent AESIs
- Listing of Subjects with Pretreatment SAEs
- Listing of Subjects with Treatment-Emergent SAEs
- Listing of Treatment-Emergent AEs that led to discontinuation of study drug
- Listing of all deaths.

9.3 Analysis of Laboratory Data

Data collected from central and local laboratories, including additional laboratory testing due to an SAE, will be used in all analyses, except for Baseline, where SAE-related laboratory assessments on or before the first dose of study drug will be excluded. The clinical laboratory tests defined in the protocol operations manual (e.g., hematology and clinical chemistry) will be summarized.

Each laboratory variable will be summarized for all time points (starting with Baseline) with the number of non-missing observations, mean and standard deviation, median, minimum and maximum.

Mean change from Baseline to each applicable post-Baseline visit will be summarized for selected laboratory variables, with the number of observations, Baseline mean, and visit mean, at each visit in Study M20-186 for each treatment group. The change from Baseline mean, standard error, and 95% confidence interval will be presented for the mean change from Baseline within each treatment group.

Shift tables will be provided for each hematology, clinical chemistry parameter. Shifts from Baseline to the following endpoints will be considered: post-Baseline value and final value. This analysis will be performed only for category of "low or normal" at Baseline which shift to 'high' and category of "high or normal" at Baseline which shift to category of 'low.'

For selected laboratory variables including hemoglobin, neutrophils, lymphocytes, platelets, creatinine, ALT, AST, CPK, LDL cholesterol, HDL cholesterol, total cholesterol, and triglycerides, a listing of all observations collected will be generated for subjects that had at least one post-Baseline observation meeting pre-defined criteria for potentially clinically important values. The number and percentage of subjects in each treatment group who have at least one post-Baseline observation meeting the pre-defined criteria for potentially clinically important values will be provided for each variable. The criteria for potentially clinically important laboratory values will be determined by NCI CTCAE version 4.03 of greater than Grade 3 or greater than Grade 4.

For the purpose of assessing for potential Hy's law cases, the frequencies and percentages of subjects with post baseline liver-specific function test values that meet the following criteria of potential clinical interest will be summarized by "as treated" treatment group:

- $ALT \geq 3 \times ULN$
- $ALT \geq 5 \times ULN$
- $ALT \geq 10 \times ULN$
- $ALT \geq 20 \times ULN$
- $AST \geq 3 \times ULN$
- $AST \geq 5 \times ULN$
- $AST \geq 10 \times ULN$
- $AST \geq 20 \times ULN$
- Total Bilirubin Level (TBL) $\geq 2 \times ULN$
- Alkaline phosphatase $\geq 1.5 \times ULN$
- ALT and/or AST $\geq 3 \times ULN$ and concurrent TBL $\geq 1.5 \times ULN$
- ALT and/or AST $\geq 3 \times ULN$ and concurrent TBL $\geq 2 \times ULN$

A listing of possible Hy's Law cases, defined as those who meet all of the following conditions simultaneously, will be provided: ALT $> 3 \times ULN$ or AST $> 3 \times ULN$ that is associated with an increase in bilirubin $\geq 2 \times ULN$ and alkaline phosphatase $< 2 \times ULN$.

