5.6 Follow-Up After Subject Discontinuation of Study Drug or from Study

To minimize missing data for efficacy and safety assessments, subjects who prematurely discontinue study drug treatment should continue to be followed for all regularly scheduled visits, unless subjects have decided to discontinue the study participation entirely (withdrawal of informed consent). Subjects should be advised on the continued scientific importance of their data even if they discontinue treatment with study drug early.

Discontinuation of Study Drug and Continuation of Study Participation

During the study, subjects may discontinue study drug treatment but may choose to continue to participate in the study. Subjects who prematurely discontinue study drug should complete a PD visit as soon as possible, preferably within 2 weeks. Afterwards, subjects should follow the regular visit schedule as outlined in Appendix D and Section 2.1 of the Operations Manual and adhere to all study procedures except for dispensing study drug. As the subject has discontinued study drug, all rescue and

efficacy discontinuation criteria may no longer apply. If at any point a subject no longer wants to provide assessments (withdrawal of informed consent) following discontinuation of study drug, a second PD visit is not required.

Premature Discontinuation from Study (Withdrawal of Informed Consent)

Subjects may withdraw from the study completely (withdrawal of informed consent) for any reason at any time. If a subject prematurely discontinues study drug treatment AND study participation (withdrawal of informed consent), the procedures outlined for the PD visit should be completed as soon as possible, preferably within 2 weeks of study drug discontinuation, and preferably prior to initiation of another therapy. In addition, if subject is willing, a 30-day follow-up call after the last dose of study drug may be completed to ensure all treatment-emergent AEs/SAEs have been resolved.

If a subject withdraws from study follow-up or withdraws permission for the collection of their personal data, the study staff may still use available public records to obtain information about survival status only, as appropriate per local regulations.

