9.0 Safety Analyses

9.1 General Considerations

Safety analyses will include reporting of adverse events, laboratory, and vital signs measurements based on data in Study M20-186. Safety analyses will be carried out using the Safety Analysis Set.

The following summary statistics will be presented for subjects who have both baseline and post-baseline values for laboratory parameters and vital signs: the mean value at Baseline and at each respective protocol specified visit, and the mean, standard deviation and median for changes from Baseline. Categorical data will be summarized using frequencies and percentages. The number of non-missing values will be given. Missing safety data will not be imputed.

For safety analysis, Baseline is defined as the last available measurement before Study M19-130 study drug administration if the subjects took active treatment in Study M19-130, and the last available measurement before Study M20-186 study drug administration if the subjects took placebo in Study M19-130.

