9.2.1 Treatment-Emergent Adverse Events

To summarize data from Study M20-186, a treatment-emergent Adverse Event (TEAE) is defined as an adverse event with an onset date that is on or after the first dose of study drug from Study M20-186, and no more than 30 days after the last dose of study drug from Study M20-186.

Events where the onset date is the same as Study M20-186 study drug start date are assumed to be treatment-emergent, unless the Study M20-186 study drug start time and the adverse event start time are collected and the adverse event start time is prior to the Study M20-186 study drug start time. If an incomplete onset date was collected for an adverse event, the event will be assumed to be treatment-emergent unless there is other evidence that confirms that the event was not treatment-emergent (e.g., the event end date was prior to the study drug start date). All treatment-emergent AEs will be summarized overall, as well as by primary MedDRA SOC and Preferred Term. The SOCs will be presented in alphabetical order, and the PTs will be presented in alphabetical order within each SOC.

The number and percentage of subjects experiencing TEAEs will be summarized.

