9.4 Analysis of Vital Signs

Vital sign measurements of systolic and diastolic blood pressure, pulse rate, body temperature, and weight will be summarized.

Each vital sign variable will be summarized for all time points with the number of non-missing observations, mean and standard deviation, median, minimum and maximum. Mean change from Baseline to each applicable post-Baseline visit will be summarized for each vital sign variable, with the number of observations, Baseline mean, and visit mean. The change from Baseline mean, standard error, and 95% confidence interval will be presented for the mean change from Baseline within each treatment group.

Vital sign variables will be evaluated based on potentially clinically important (PCI) criteria ([Appendix C](#)). For each vital sign PCI criterion, the number and percentage of subjects who have a vital sign value meeting the criteria will be summarized. Listings will be provided to summarize subject-level vital sign data for subjects meeting PCI criteria.

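### For subjects who stop study drug but stay in follow-up, laboratory, vital-sign and QTcF values have no last-dose limit, so off-drug values enter the by-treatment safety tables

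*SAP*

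**What the plan says.** SAP 9.1 bounds the safety data by study only: "Safety analyses will include reporting of adverse events, laboratory, and vital signs measurements based on data in Study M20-186". SAP 9.3 adds that central and local laboratory results, "including additional laboratory testing due to an SAE, will be used in all analyses"; its one exception concerns Baseline. The laboratory outputs are then:

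- summaries at every time point, and change by visit: "Mean change from Baseline to each applicable post-Baseline visit will be summarized for selected laboratory variables";
- shift tables: "Shifts from Baseline to the following endpoints will be considered: post-Baseline value and final value", with final value left undefined;
- counts of subjects with any qualifying value after Baseline, for the potentially clinically important (PCI) criteria and the liver criteria.

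SAP 9.4 treats vital signs the same way; for the PCI criteria, "the number and percentage of subjects who have a vital sign value meeting the criteria will be summarized". SAP 9.6 counts QTcF above 500 msec by treatment group. None of the three sections gives an end date.

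Adverse events do have one. Under SAP 9.2.1 the onset must be "no more than 30 days after the last dose of study drug from Study M20-186".

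Protocol 5.5 asks subjects who stop study drug early to remain in the study if possible. Protocol 5.6 has them complete a premature discontinuation (PD) visit, and then: "Afterwards, subjects should follow the regular visit schedule as outlined in Appendix D", with every procedure except dispensing. Protocol Appendix D places chemistry, haematology and vital signs at every visit to Week 104, and ECGs at Weeks 64, 80 and 96. Subjects in a group discontinued by the sponsor take a different route: a PD visit and a 30-day telephone call.

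**The concern.** Safety is the primary objective, and protocol 4.2 sets the main comparison against each group's safety profile in the randomised study. The laboratory and vital-sign tables should therefore describe what happens on each regimen. A value taken months after the last dose describes something else, and it can mislead in two directions.

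- **Means and final-value shifts.** An effect that reverses off drug is averaged with values from which it has gone. This need not be random: protocol 5.5 and Table 4 make some laboratory abnormalities reasons for stopping. A subject who stops for such an abnormality, recovers and attends Week 104 contributes a recovered final value, so the abnormality drops out of that shift.
- **Any-value counts.** An abnormality that first arises off drug is added to the treatment group. It may arise under new therapy: protocol 5.5 names cyclophosphamide, rituximab and high-dose steroids among introductions that require stopping. Under SAP 7.3, medication started more than one day after the last dose is not tabulated as concomitant, so the tables would not show the new therapy beside the laboratory count.

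**Working it through.** **1. Where each data type ends**

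| Data | Source | End of window |
|---|---|---|
| Treatment-emergent AEs | SAP 9.2.1 | last dose + 30 days |
| Exposure, and AE-rate denominator | SAP 6.0, 9.2.4 | last dose |
| Concomitant medication | SAP 7.3 | last dose + 1 day |
| Laboratory | SAP 9.3 | none stated |
| Vital signs | SAP 9.4 | none stated |
| QTcF | SAP 9.6 | none stated |

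**2. Length of follow-up.** SAP 2.3 gives a 56-week period from Week 48 to Week 104. Check: 104 − 48 = 56 weeks, or 56 × 7 = 392 days. This reproduces the plan's figure. Scheduled visits after Week 48 are Weeks 56, 64, 72, 80, 88, 96 and 104, which is 7 for laboratory and vital signs. ECG has 3: Weeks 64, 80 and 96.

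**3. Visits beyond the AE window.** For a last dose at Week s, a visit at Week w falls 7 × (w − s) days later and is outside the window if that exceeds 30. The stopping weeks are assumptions.

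| Last dose (week) | Lab/vital visits outside, of 7 | Days off drug at Week 104 | ECGs outside, of 3 | Days off drug at Week 96 ECG |
|---|---|---|---|---|
| 50 | 7 | 378 | 3 | 322 |
| 56 | 6 | 336 | 3 | 280 |
| 72 | 4 | 224 | 2 | 168 |
| 88 | 2 | 112 | 1 | 56 |
| 96 | 1 | 56 | 0 | 0 |

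For the Week 72 stop, Weeks 80, 88, 96 and 104 fall 56, 112, 168 and 224 days after the last dose; 4/7 = 57%. The ±7-day visit window does not rescue the nearest one: 56 − 7 = 49 days, still more than 30.

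**4. Effect on a visit mean.** Let f be the share of values at a visit that are off drug, D the mean change among subjects still on drug, and r the fraction of D still present in the off-drug values. Then

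observed mean change = (1 − f) × D + f × r × D, so shrinkage relative to D = f × (1 − r).

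| f (assumed) | D retained, full reversal (r = 0) | D retained, half reversal (r = 0.5) |
|---|---|---|
| 5% | 95% | 97.5% |
| 10% | 90% | 95% |
| 20% | 80% | 90% |
| 30% | 70% | 85% |

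Full reversal is the upper bound on dilution, provided off-drug values do not pass beyond Baseline in the other direction. The documents supply neither f nor r.

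**5. Effect on any-value counts.** Subjects with a qualifying value inside a window are a subset of those with a qualifying value at any time. Open-ended data can therefore raise the PCI, liver and QTcF counts but never lower them.

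**The case against.** The strongest reply is that this is an unstated window in a descriptive study with no hypothesis test, and that existing outputs limit the harm. Much of that is fair.

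- **Labelling.** A reader might infer that the SAP declares off-drug values to be on-drug data. It does not. The mixing follows from silence on an end date combined with tabulation by treatment group.
- **Who is affected.** A reader might infer that everyone who stops is followed to Week 104. Continued attendance is requested where possible and is the subject's choice, and sponsor-discontinued groups yield little off-drug laboratory data. The point is confined to individual stoppers who stay.
- **Missing adverse events.** It is tempting to argue that a late PCI value without a matching treatment-emergent event exposes an inconsistency. That argument is weak. Under protocol 6.1 a laboratory abnormality is an adverse event only in certain circumstances, so unmatched PCI values are expected on drug too.
- **Existing safeguards.** SAP 9.3 lists all observations for subjects with a PCI value in the selected laboratory variables and lists possible Hy's Law cases; SAP 9.4 has a similar vital-sign listing. The shift tables also have a post-Baseline endpoint, where an on-drug shift that later reverses can still appear. Extra events in any-value counts err on the cautious side.
- **ECG.** Exposure is small: three scheduled visits and one threshold.
- **The remedy.** A 30-day tail still admits some off-drug values, and a last-dose rule does not address temporary interruptions. All-data and on-treatment summaries are both defensible if labelled.

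What remains is that the listings do not correct the visit means or the final-value shifts, and no section tells the programmer or the reader which period the tables cover.

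**Conclusion.** The concern holds in this limited form. As written, SAP 9.3, 9.4 and 9.6 would combine on-drug values with values taken up to about a year after the last dose (378 days for a stop at Week 50), in tables that serve the primary objective. Visit means and final-value shifts can be diluted. Any-value counts can only gain events.

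The per-subject arithmetic is exact for a given stopping week. The overall size is unknown, because the documents give no discontinuation rate and no rate of continued attendance off drug. A reader might take a 10% to 30% understatement of mean changes from the table of f. The documents do not support that as an estimate: it restates an assumed off-drug share and also requires complete reversal, and nothing in either document describes recovery of these parameters after stopping. The SAP should be changed, but the gap does not invalidate the safety analysis.

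**What to change.** In SAP 9.3, 9.4 and 9.6:

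- base the main means, shift tables, PCI counts, liver-criteria counts and QTcF count on values taken up to 30 days after the last M20-186 dose, matching SAP 9.2.1;
- define the final value as the last value in that window;
- list later values separately with days since last dose, or keep the all-data tables as supplementary and label them so.

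If a programming convention already applies such a window, it should be written into the SAP.

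The cost is a few sentences and a date filter. The downside is fewer observations in the main tables at late visits. A PD visit held within the preferred 2 weeks of stopping stays inside the window, so the assessment closest to discontinuation is kept. A delayed abnormality remains visible in the listing. Temporary interruptions are not covered by this rule and would need their own sentence if the sponsor wants them handled.

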Subjects must be discontinued from study drug for an ECG change considered clinically significant and with reasonable possibility of relationship to study drug OR a confirmed absolute QTcF value > 500 msec or confirmed increase of ≥ 60 msec from Baseline.

Management of Muscle-Related Symptoms

If a subject experiences symptoms suggestive of myositis or rhabdomyolysis, CPK and aldolase measurements should be requested and will be provided after review by the AbbVie TA MD with clinical management and/or study drug interruption as deemed appropriate by the treating physician. Please refer to Table 4 below for further instructions.

Management of Thrombosis Events

Subjects who develop symptoms of thrombosis should be promptly evaluated and treated appropriately. If the diagnosis of deep vein thrombosis, pulmonary embolus, or non-cardiac, non-neurologic arterial thrombosis is confirmed, the subject must be discontinued from study drug.

Management of Select Laboratory Abnormalities

For any given laboratory abnormality, the investigator should assess the subject and apply the standard of care for medical evaluation and treatment following any local guidelines. Specific toxicity management guidelines for abnormal laboratory values are described in Table 4 and may require a supplemental eCRF to be completed (see Section 6.1). All abnormal laboratory tests that are considered clinically significant by the investigator will be followed to a satisfactory resolution. If a repeat test is required per Table 4, the repeat testing must occur as soon as possible.

Table 4. Specific Toxicity Management Guidelines for Abnormal Laboratory Values

| Laboratory Parameters | Toxicity Management Guidelines | |
|---------------------------------|--|--|
| Hemoglobin | If hemoglobin < 8 g/dL, interrupt study drug dosing and confirm by repeat testing with a new sample. | |
| | If hemoglobin decreases ≥ 3.0 g/dL from Baseline without an alternative etiology, interrupt study drug dosing and confirm by repeat testing with new sample. | |
| | • If hemoglobin decreases ≥ 3.0 g/dL from Baseline and an alternative etiology is known, the subject may remain on study drug at the investigator's discretion. | |
| | If confirmed, continue to withhold study drug until hemoglobin value returns to normal reference range or its baseline value. | |

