| Absolute neutrophil count (ANC) | If confirmed < 750 cells/ μ L by repeat testing with new sample, interrupt study drug dosing until ANC value returns to normal reference range or its baseline value. Subjects who meet this criterion should be evaluated for an alternative etiology and closely monitored for infections. | |
| | The alternative etiology should be documented appropriately in the eCRF. If restarting study drug, documentation should include the reason rechallenge is expected to be safe. | |
| Platelet count | If confirmed < 30,000 platelets/μL by repeat testing with new sample, interrupt study drug dosing until platelet count returns to normal reference range or its baseline value. | |

| Laboratory Parameters | Toxicity Management Guidelines |
|--|---|
| Aspartate transaminase (AST) or alanine transaminase (ALT) | Interrupt study drug immediately if confirmed ALT or AST > 3 × ULN by repeat testing with new sample and either a total bilirubin > 2 × ULN or an INR > 1.5. |
| | INR will only need to be measured in subjects with ALT or AST > 3 × ULN by the central laboratory. A repeat test of INR is not needed for determination if above toxicity management criteria are met. |
| | • Interrupt study drug immediately if confirmed ALT or AST > 3 × ULN by repeat testing with new sample along with appearance of fatigue, nausea, vomiting, right upper quadrant pain, or tenderness, fever, rash, and/or eosinophilia (> 5%). |
| | Interrupt study drug immediately if ALT or AST > 5 × ULN by repeat testing with new sample. |
| | Interrupt study drug immediately if ALT or AST > 8 × ULN and contact the AbbVie TA MD. |
| | Subjects who meet any of the above criteria should be evaluated for an alternative etiology of the ALT or AST elevation and managed as medically appropriate. The investigator should contact the AbbVie TA MD to discuss the management of a subject when an alternative etiology has been determined. The alternative etiology should be documented appropriately in the eCRF; study drug should be discontinued if no alternative etiology can be found. |
| | For any confirmed ALT or AST elevations > 3 × ULN, complete supplemental hepatic eCRF. |
| | Subjects with HBc Ab+ status (irrespective of HBs Ab status) and negative HBV DNA at Study M19-130 Screening who develop the following should have HBV DNA by PCR testing performed within 1 week: |
| | • ALT > 5 × ULN OR |
| | ALT or AST > 3 × ULN if an alternative cause is not readily identified. |

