| | A positive result for HBV DNA PCR testing in these subjects will require immediate interruption of study drug (per local guidelines) and a hepatologist consultation should occur within 1 week for recommendation regarding subsequent treatment. |
| Serum Creatinine | • If serum creatinine is > 1.5 × the baseline value and > ULN, repeat the test for serum creatinine (with subject in an euvolemic state) to confirm the results. If the results of the repeat testing still meet this criterion then interrupt study drug and re-start study drug once serum creatinine returns to ≤ 1.5 × baseline value and ≤ ULN. |
| | If confirmed new serum creatinine ≥ 2 mg/dL, interrupt study drug and re-start study drug once serum creatinine returns to normal reference range or its baseline value. |
| | For the above serum creatinine elevation scenarios, complete supplemental renal eCRF(s). |

| Laboratory Parameters | Toxicity Management Guidelines |
|-----------------------------------|--|
| Creatine Phosphokinase (CPK) | CPK and aldolase will be measured at every visit, but results will be blinded to sites and subjects, as CPK elevation is a known class effect of JAK inhibitors and the results could be unblinding to the sites. If symptomatic myositis is suspected, the site may send a request to the AbbVie TA MD for CPK and/or aldolase results to be unblinded. Request must be approved by the AbbVie TA MD. |
| | If confirmed CPK ≥ 4 × ULN accompanied by symptoms suggestive of myositis or rhabdomyolysis, interrupt study drug, complete supplemental CPK eCRF, and contact the AbbVie TA MD. |
| Lymphocyte Count Decreased | • If confirmed Grade 4 (< 200/mm³) by repeat testing with new sample, interrupt study drug dosing until lymphocyte count returns to at least Grade 2 (< 800 to 500/mm³) or its baseline value. |
| White Blood Count Decreased | If confirmed Grade 4 (<1000/mm³) by repeat testing with new sample, interrupt study drug dosing until white blood cell count returns to at least Grade 2 (< 3000 to 2000/mm³) or its baseline value. |
| Urine Protein to Creatinine Ratio | If > 2 g/day equivalent (2 mg/mg), repeat by testing with new sample, and if confirmed, a renal biopsy will be required. |
| | If Class IV lupus nephritis is confirmed, subject must be permanently discontinued from study drug. |

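### SAP 9.3 shift tables count only new abnormality, so worsening from an already abnormal Baseline that stays below the PCI threshold is in no systematic subject-level count

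*SAP*

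**What the plan says.** SAP Section 9.3 sets out several laboratory summaries.

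- **Shift tables.** "Shift tables will be provided for each hematology, clinical chemistry parameter". The analysis is "performed only for category of 'low or normal' at Baseline which shift to 'high' and category of 'high or normal' at Baseline", the second category being for shifts to low. Shifts are taken to the post-Baseline value and to the final value.
- **PCI table.** The number and percentage of subjects who "have at least one post-Baseline observation meeting the pre-defined criteria for potentially clinically important values will be provided for each variable" are tabulated, and all observations of those subjects are listed. The variables are introduced as including "hemoglobin, neutrophils, lymphocytes, platelets, creatinine, ALT, AST, CPK, LDL cholesterol, HDL cholesterol, total cholesterol, and triglycerides". The criterion is "determined by NCI CTCAE version 4.03 of greater than Grade 3 or greater than Grade 4".
- **Liver table.** Subjects with ALT or AST at or above 3, 5, 10 and 20 x ULN are counted, with rows for bilirubin and alkaline phosphatase.
- **Group-level summaries.** Each variable is described by visit, including minimum and maximum, and mean change from Baseline is given for selected variables.

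Protocol Section 6.1 treats a laboratory abnormality as an adverse event only if it leads to discontinuation, needs therapeutic intervention, meets a criterion in Section 6.2, or is judged to be one by the investigator.

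**The concern.** The shift tables describe only subjects who start normal, or abnormal in the opposite direction. A subject who enters with a low lymphocyte count, or a high CPK or ALT, cannot contribute to the row that would show further deterioration.

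The protocol allows for such subjects. In Table 4 the neutrophil rule is to "interrupt study drug dosing until ANC value returns to normal reference range or its baseline value", and the lymphocyte rule is to "interrupt study drug dosing until lymphocyte count returns to at least Grade 2" or, again, the baseline value. Table 4 also uses change from Baseline as a trigger for hemoglobin and creatinine, and the vital-sign PCI criteria in SAP Appendix C include change from Baseline. The laboratory PCI criterion is stated only as a grade.

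Longer-term safety is the primary objective. Anemia, neutropenia and lymphopenia are adverse events of special interest, and the protocol lists them among the potential risks of upadacitinib. Group means do not show individual deterioration. The safety Baseline also differs by history (SAP Section 9.1): it precedes M19-130 for subjects who took active drug there and precedes M20-186 for former placebo subjects. The share unable to register a shift may therefore differ between Groups 1 to 4 and Groups 5a and 5b.

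**Working it through.** The plan gives no figure on this point, so the check applies its own rules to every possible case.

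**Inputs.** The shift rule, PCI rule and liver rows come from SAP 9.3. The lymphocyte limits come from Protocol Table 4: Grade 2 is below 800 down to 500/mm³ and Grade 4 is below 200/mm³, so Grade 3 lies between 200 and 500. Assumption: a value outside the normal range is at least Grade 1.

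**Step 1: list the transitions.** With Baseline at Grade 1, 2 or 3 and a worse grade up to 4 afterwards, there are 3 + 2 + 1 = 6.

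**Step 2: apply each rule.** The PCI wording can be read as Grade 3 or above, or literally as above Grade 3, which is Grade 4. Taken alone, the phrase about exceeding Grade 4 would leave only Grade 5, which is death, and would count none of the six.

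| Baseline to worst grade | Shift table | PCI, Grade 3 or above | PCI, Grade 4 only |
|---|---|---|---|
| 1 to 2 | no | no | no |
| 1 to 3 | no | yes | no |
| 1 to 4 | no | yes | yes |
| 2 to 3 | no | yes | no |
| 2 to 4 | no | yes | yes |
| 3 to 4 | no | yes | yes |
| **Counted** | **0 of 6** | **5 of 6** | **3 of 6** |

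These are types of transition, not subjects: 1 of 6 uncounted does not mean one sixth of events.

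**Step 3: lymphocytes.**
- *700 to 300/mm³* (Grade 2 to 3): a fall of (700 − 300)/700 = 57%. It is not a shift, and is PCI only on the Grade 3-or-above reading.
- *700 to 150/mm³* (Grade 2 to 4): not a shift, but PCI on either reading.
- *950 to 520/mm³*: a fall of (950 − 520)/950 = 45%. With a lower limit of normal of 1000/mm³ (assumed; any limit above 950 gives the same answer) the subject is already low, so there is no shift. The value of 520 is Grade 2, so it is not PCI on either reading. Table 4 acts only on a confirmed Grade 4 count, so no Section 6.2 criterion is met. If the limit were between 520 and 950, the fall would count as a new shift.

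**Step 4: liver enzymes.** ALT from 1.5 to 4 x ULN enters the 3 x ULN row, and from 2.5 to 6 x ULN enters the 3 and 5 x ULN rows. From 1.5 to 2.5 x ULN enters no row.

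**Step 5: CPK and white cells.** CPK is a PCI variable but has no table like the one for liver tests. Table 4 keeps its results blinded to sites and acts only on a confirmed value of at least 4 x ULN with symptoms. An asymptomatic rise below the PCI grade would therefore not normally reach the investigator. Total white cell count has its own rule in Table 4 but is not named among the PCI variables, so its inclusion depends on how the opening word of that list is read.

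**The case against.** A reader might infer from the shift restriction that worsening in a subject who starts abnormal is counted nowhere. The documents do not support that. The PCI and liver tables carry no Baseline condition, so anyone who reaches their thresholds is counted, although not identified as having worsened.

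The adverse-event route matters too. A hemoglobin fall of at least 3.0 g/dL triggers Table 4, where the instruction for a fall "from Baseline without an alternative etiology, interrupt study drug dosing and confirm by repeat testing with new sample" applies. Under Protocol 6.1, meeting such a criterion makes the change an adverse event. It then enters the TEAE tables and, if coded to an anemia term, the anemia AESI summary. A confirmed creatinine above 1.5 times baseline and above ULN is covered in the same way, even in a subject who starts high. Hemoglobin falls of that size therefore do not illustrate the gap.

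It can also be said that tabulating new abnormality is a legitimate display in a descriptive study with no hypothesis, and that subjects abnormal at Baseline stay in the visit summaries and mean changes. Both statements are true. But those summaries are group-level, and below the PCI and liver thresholds and the Table 4 criteria the adverse-event route depends on an intervention, a discontinuation or the investigator's judgment. That is not a systematic count, and for blinded CPK it is weaker still.

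**Conclusion.** The point holds within limits. Worsening from an abnormal Baseline is never a shift under SAP 9.3. It is counted elsewhere only on reaching the PCI grade or a liver-table row, or on being reported as an adverse event. Below those limits it is in no systematic subject-level count. The uncounted transitions are Grade 1 to 2 if PCI means Grade 3 or above, and also 1 to 3 and 2 to 3 if the wording is literal, apart from ALT or AST values that reach a liver row. The unclear PCI wording thus sets much of the gap's size.

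It is tempting to put a headcount on this, but the documents do not give the share of subjects abnormal at Baseline, and Table 4's references to a baseline value imply no prevalence. The number affected cannot be derived. The conclusion rests on equating low or high with being outside the normal range and at least Grade 1; the 950 to 520/mm³ example also needs the assumed lower limit. This is a cheap improvement to the primary safety display and does not invalidate the analysis.

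**What to change.** Three changes to SAP 9.3:

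1. For hemoglobin, neutrophils, lymphocytes, white cells, platelets, ALT, AST, creatinine and CPK, tabulate Baseline CTCAE grade by worst post-Baseline grade. Include every subject with a Baseline and at least one post-Baseline value, and report the number worsening by at least 1 and by at least 2 grades.
2. For analytes without grades, show the full 3 x 3 table of low, normal and high.
3. Replace the two-part PCI wording with one unambiguous grade threshold, and say whether total white cell count is a PCI variable.

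The cost is SAP text, a standard table shell and slightly larger tables. No new data are needed, grading is already required for most of these analytes under the PCI criterion, and clinical management is untouched.
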